### 2. Specific Aims:

1. Development of an ESM questionnaire specifically tailored to the unique circumstances psychiatric patients face during their hospitalization.

2. Investigation of the feasibility and compliance of patients in participating in the study, including their willingness to complete digital ESM questionnaires three times a day and wear the smartwatch sensor throughout their hospitalization. Additionally, we will explore potential differences in adherence and compliance among subjects with different psychiatric diagnoses regarding their willingness to participate in the study, complete self-report ESM questionnaires, and wear the smartwatch.
3. Examination of the validity of the ESM questionnaire in predicting the trends of change in symptom severity among psychiatric patients during a 14-day psychiatric hospitalization period. This validity will be evaluated by comparing the trends in symptom severity as measured by the ESM questionnaire with the trends observed in four PANSS assessments conducted throughout the hospitalization.
4. The validity of subjects' self-reports on sleep quality and activity level will be assessed by comparing the self-report ESM data with the physiological indicators collected by the smartwatch. Additionally, the ESM indices will be compared to reports from the nursing staff on the ward. Furthermore, we will explore whether these comparisons yield different outcomes among subjects with different psychiatric diagnoses.
5. The effectiveness of the monitoring model will be assessed by examining the impact of exposing the psychiatrists to ESM data, as well as the physiological indicators collected by the smartwatch, on the decision-making process regarding changes in the patient's medication plan during psychiatric hospitalization.
6. Patient satisfaction:

Assessing patient satisfaction with the monitoring model used throughout their 14-day hospitalization. Following the monitoring period, subjects will be asked to provide feedback on their satisfaction levels through questionnaires.

7. The satisfaction of the multi-disciplinary teams (physicians, nursing staff, clinical psychologists, social workers, occupational therapists):

At the end of the study, the teams will report through questionnaires on their satisfaction with using this monitoring model and its influence on the team's clinical decision-making.

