### **Participants**

To conduct the monitoring model, we will recruit 100 subjects hospitalized in the inpatient wards. To receive feedback on implementing the monitoring model from the multi-disciplinary care team working in the wards, we will recruit 30 multi-disciplinary team members. The running will be carried out in two stages:

- Pre-Test - 20 patients and feedback from 5 multi-disciplinary – estimated time – 3 months.
- Field Test - 80 additional patients and feedback from 30 multi-disciplinary staff members – estimated 12 months.

The study inclusion criteria for the patients: adults are consenting hospitalized in a psychiatric hospital at the Sheba Medical Center in the open part of the ward who owns a mobile smartphone. Exclusion criteria: patients with a low level of treatment compliance, patients with a developmental or intellectual disability, complex organic conditions including dementia, patients who cannot read and write in the Hebrew language, and patients who are incapable of informed consent.

The study inclusion criteria for the multi-disciplinary team: multi-disciplinary team members who work in the psychiatric inpatient wards at the Sheba Medical Center. The staff members will have a valid Israeli license (from the professions of medicine, nursing, psychology, social work, and occupational therapy).

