- 6. The effect of exposing the psychiatrists to the patient's monitoring indicators on their clinical decisions regarding him will be examined in a short questionnaire that the physician will fill out after each medication change and mark on a Likert scale of 1-5 - how much the exposure to the monitoring indicators influenced the clinical decision.
- 7. Patient satisfaction: After 14 days of monitoring, the subjects will report their satisfaction with using the monitoring model throughout the hospitalization through questionnaires.
- 8. The satisfaction of the multi-disciplinary teams: At the end of the study, the teams will report through questionnaires on their satisfaction with using this monitoring model and its influence on the team's clinical decision-making.

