## **Research Process**

After recruiting the patient for the study and signing informed consent, the monitoring application (Datos Health) and the wearable smartwatch application (Garmin) will be installed on the patient's smartphone. The patient will receive an extensive explanation from the research team's representative on the self-reporting method and will experience using the application.

From this stage, the hospitalized subject will receive ongoing clinical care, alongside participation in monitoring indicators by self-reporting in the ESM questionnaires using the Datos Health application and physiological indices monitoring by using the Garmin smartwatch. The trial will end after 14 days or until the patient's discharge (whichever comes first). The ESM self-report sampling will be conducted a frequency of 3 times a day in a semi-random manner:

- The first sample will be randomly sampled between 8-10 am.
- A second sample will be randomly sampled between 1-3 pm.
- A third sample will be randomly sampled between 7-10 pm.

In each clinical discussion of the subject's mental state, the ward staff will watch the dashboard of the Datos Health application, which will display the subject's self-report measures and physiological indicators. For each change in the patient's clinical status, determined by the physician (change of medication, vacation, preparation for discharge, discharge), the physician will answer a questionnaire in which he will document how much (between 1-5) the clinical decision was influenced by the monitoring indicators he observed.

The feasibility and compliance, Validity, and changes in the patient's condition over timeline indicators will be collected for 14 days and analyzed at the study's end. The patient satisfaction indicators will be tested after 14 days of monitoring through a questionnaire sent to each subject. The satisfaction indicators of the clinical staff in the ward will be tested through questionnaires sent to the clinical staff at the end of the study.

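### Patient satisfaction is timed after 14 days of monitoring, a point that patients discharged before day 14 never reach, so when or whether they are asked is undefined

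*Protocol*

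**What the plan says.** Four statements in the Protocol bear on this.

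- **End of participation** (phase 2 Research Process): "The trial will end after 14 days or until the patient's discharge (whichever comes first").
- **Timing of the questionnaire** (same section): "The patient satisfaction indicators will be tested after 14 days of monitoring through a questionnaire sent to each subject".
- **Timing again** (Field test indices, item 7): "After 14 days of monitoring, the subjects will report their satisfaction with using the monitoring model throughout the hospitalization through questionnaires".
- **The aim itself** (Specific Aims, Aim 6): "Assessing patient satisfaction with the monitoring model used throughout their 14-day hospitalization". The next sentence reads: "Following the monitoring period, subjects will be asked to provide feedback on their satisfaction levels through questionnaires".

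On numbers, the phase 2 Participants section says "we will recruit 100 subjects hospitalized in the inpatient wards", made up of 20 in the pre-test and 80 in the field test. No section describes a satisfaction assessment at discharge, and none gives an expected early-discharge rate.

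**The concern.** The rule for ending participation allows for early discharge; the rule for measuring satisfaction does not. Both operational statements hang the questionnaire on a time point that exists only for patients who stay the full period. Staff following the text have no instruction for a patient discharged on, say, day 8.

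Aim 6 is at stake. If early-discharged patients are not asked, the satisfaction result describes only those who stayed. If they are asked at calendar day 14, they answer away from the ward and from memory, while completers answer just as monitoring ends. The Protocol's own introduction criticises reports from memory as prone to bias. The questionnaire's timing belongs to the assessment schedule, which the protocol fixes, and no later analysis can recover answers that were not collected.

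**Working it through.** The Protocol states no figure on this point, so there is none to reproduce. The check is a comparison of the text, followed by an illustration.

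**Step 1. Apply the rules to two patients.**

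| Patient | Participation ends | 14 days of monitoring reached? | Questionnaire under Research Process and item 7 | Under Aim 6 |
|---|---|---|---|---|
| Stays to day 14 | Day 14 | Yes | At day 14 | At day 14 |
| Discharged on day 6 (example) | Day 6 | No | Not triggered, or at calendar day 14 | After day 6 if the monitoring period is the patient's own; unclear if it is the 14-day period named in the sentence before |

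On the calendar reading, the second patient is asked 14 − 6 = 8 days after monitoring stopped. So there are three possible outcomes for this patient, and the text does not choose among them.

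**Step 2. What non-assessment could do to the estimate.** Let *d* be the share discharged early and not asked, *p*c the proportion satisfied among completers, and *p*e the proportion satisfied among early leavers. All three are assumptions.

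- Satisfaction in all patients = *p*c(1 − *d*) + *p*e·*d*
- Reported minus actual = *p*c − [*p*c(1 − *d*) + *p*e·*d*] = *d*(*p*c − *p*e)

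The sign is that of *p*c − *p*e, about which the Protocol says nothing. With *p*c = 0.80, the bounds take *p*e = 0 and *p*e = 1:

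| *d* | Lower bound | Upper bound | If *p*e = 0.50 |
|---|---|---|---|
| 10% | 0.80 × 0.90 = 72% | 72% + 10% = 82% | 72% + 5% = 77% |
| 20% | 0.80 × 0.80 = 64% | 64% + 20% = 84% | 64% + 10% = 74% |
| 40% | 0.80 × 0.60 = 48% | 48% + 40% = 88% | 48% + 20% = 68% |

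The reported figure would be 80% in every row. It lies inside each pair of bounds, so the error could go either way.

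**Step 3. Precision.** The 95% half-width is 1.96·√[*p*(1 − *p*)/*n*] with *p* = 0.80: 7.8 points for *n* = 100, 8.8 for *n* = 80 (*d* = 20%) and 10.1 for *n* = 60 (*d* = 40%). The loss of precision is modest; the unknown answers of those not asked matter more. If only the 80 field-test patients count, the percentages in Step 2 do not change.

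**The case against.** The strongest reply is that the Protocol plainly means to ask everyone. The questionnaire goes to each subject, Aim 6 places it after the monitoring period, and that period ends at discharge for an early leaver. Every patient must own a smartphone, so a discharged patient can be reached. The Protocol also uses 14 days as a nominal length elsewhere: the same paragraph says that other indicators are collected for 14 days, and nobody would take that to discard data from patients discharged early.

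Much of this stands. A reader might infer that satisfaction will be measured in completers only; no sentence says so, and the intention looks to be the opposite. A reader might also infer that patients who stop answering or wearing the watch are lost. The text does not support that: discharge is the only early end it states, low response and low wear are themselves feasibility outcomes, and a patient still on the ward at day 14 is still a subject who is sent the questionnaire. Nor does anything show that early discharge signals dissatisfaction, so a claim of upward bias is unsupported.

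What does not stand is that the intention settles the timing. A nominal 14 days does no harm for data gathered along the way, because a shorter stay simply gives less. It does matter for a single assessment placed at the end of that interval, because a shorter stay leaves no such point. Aim 6 could supply one, but it also speaks of a 14-day hospitalization, and the two operational statements do not repeat its wording.

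**Conclusion.** The point holds as a timing conflict inside the Protocol. Patients discharged before day 14 never reach the stated time of the satisfaction questionnaire, and the text leaves them either unasked or asked late and under different conditions. This may bias Aim 6.

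Neither direction nor size can be determined. The figures of 80% and 50% satisfied and the early-exit shares are assumptions, and they show only the scale: at 20% early exit without assessment, the possible values run from 64% to 84% around a reported 80%. If early leavers are in fact asked at calendar day 14 and reply, the problem is one of delay and setting, and these bounds do not apply.

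Aim 6 is one of seven specific aims, and the primary objective, validation against the PANSS, is untouched. The change is still worth making, because it is nearly free now and answers not collected cannot be recovered later.

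**What to change.** In the phase 2 Research Process section and in item 7 of the Field test indices, replace the 14-day trigger with the end of each patient's own participation, and bring Aim 6 into line. Suggested wording:

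> The satisfaction questionnaire is sent to every enrolled patient when that patient's participation ends, at day 14 or at discharge, whichever is earlier, regardless of how many ESM questionnaires were answered or how long the watch was worn. Satisfaction is reported together with the number of days monitored.

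This uses the participation rule that the Protocol already contains and adds no visit. The cost is a change of wording and of the send date. The one downside is that patients will judge the model after different lengths of exposure, which reporting the days monitored makes visible.

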## **Place of conducting the research**

The research will be carried out at the psychiatric inpatient wards A, B, and C in the psychiatric division at the Sheba Medical Center.

## Ethics

The study was approved by the Helsinki Committee of the Sheba Medical Center.
